9.3 VARIABLES

9.3.1 Exposures

Patients in this study will have been prescribed a treatment for their COPD. They could have been prescribed ICS or not. Prescription of the treatments will have been done under the sole responsibility of the healthcare professional and before the study initiation visit.

In addition, no intervention, either diagnostic or therapeutic, will be applied to patients other than that used for routine clinical practice.

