7.2.11 Risk stratification

Patients will be classified according to their risk based on GesEPOC 2017 Spanish guideline:

- Low risk:
 - FEV₁(%) post-bronchodilation ≥ 50% and,
 - mMRC 0-2, and
 - 0 or 1 exacerbation in the last year, and
 - without hospitalization in the last year.
- High risk:
 - FEV₁(%) post-bronchodilation <50% or,
 - mMRC > 2 or mMRC = 2 with treatment or,
 - 2 or more exacerbation in the last year or,
 - 1 or more exacerbation with hospitalization in the last year.

Document: \\bcnfs02\general\Hdmgener\MEDICAL AFFAIRS 28.02.2017 actualizada\8. SRO ESTUDIOS\RESPIRATORIO\1237-0070 NIS OPTI\11 - Clinical Trial Report\SAP\SAP - V 1.0\SAP OPTI version1.0 29052019.docx

Author: Version Number: 1.0

Version Date: [29MAY2019]

Template No.: RWI_TP_BIOS0013 Revision 1

Reference: RWI_WI_BIOS0015

Effective Date: 15Jun2018

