Phenotype, obtained from Figure 4 in “Guía española de la enfermedad pulmonar obstructiva crónica (GesEPOC) 2017. Tratamiento farmacológico en fase estable” in

<http://www.archbronconeumol.org/es-pdf-S0300289617300844>.

Document: \\bcnfs02\general\Hdmgener\MEDICAL AFFAIRS 28.02.2017 actualizada\8. SRO ESTUDIOS\RESPIRATORIO\1237-0070 NIS OPTI\11 - Clinical Trial Report\SAP\SAP - V 1.0\SAP OPTI version1.0 29052019.docx

Author: Version Number: 1.0
Version Date: [29MAY2019]

[figure not shown]
Template No.: RWI_TP_BIOS0013 Revision 1 Reference: RWI_WI_BIOS0015

Effective Date: 15Jun2018

The use of ICS is indicated only in these cases:

- Patients at high risk and,
 - Phenotypes: exacerbator with emphysema, exacerbator with chronic bronchitis or mixed COPD - asthma syndrome (ACOS). Only mixed phenotype allows the use of ICS as the first option. For exacerbator with chronic bronchitis and exacerbator with emphysema, the use of ICS is indicated after a first treatment of LAMA / LABA, when there is worsening of symptoms.

Table D: Treatment COPD scheme according to risk and phenotype

Document: \\bcnfs02\general\Hdmgener\MEDICAL AFFAIRS 28.02.2017 actualizada\8. SRO ESTUDIOS\RESPIRATORIO\1237-0070 NIS OPTI\11 - Clinical Trial Report\SAP\SAP - V 1.0\SAP OPTI version1.0 29052019.docx

Author:

Version Number: 1.0

Version Date: [29MAY2019]

Template No.: RWI_TP_BIOS0013 Revision 1

Reference: RWI_WI_BIOS0015

Effective Date: 15Jun2018

Copyright © 2018 All rights reserved. The contents of this document are confidential and proprietary to subsidiaries. Unauthorized use, disclosure or reproduction is strictly prohibited.

Holdings Inc. and its

[figure not shown]

Figure 4 in “Guía española de la enfermedad pulmonar obstructiva crónica (GesEPOC) 2017. Tratamiento farmacológico en fase estable” (<http://www.archbronconeumol.org/es-pdf-S0300289617300844>)

Taking into account the algorithm of treatment recommendations included in GesEPOC (phenotype) guidelines, we will define patients as:

- Adherent to ICS (Adequate use of ICS):
 - Patients treated with ICS that according to GesEPOC guidelines should have been treated with ICS, or
 - Patients **not** treated with ICS that according to GesEPOC guidelines should **not** have been treated with ICS.
- Non-Adherent to ICS (Inadequate use of ICS):
 - Patients treated with ICS but according to GesEPOC guidelines should **not** have been treated with ICS, or

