16.1.3.1 Current treatment with ICS

Main variable will be presented according to the presence or not of moderate/severe exacerbations in the previous 365 days.

The use of ICS will be analyzed using number of patients in each category and percentages (absolute and relative frequencies) and 95% confidence intervals will be provided based on Wald's (Normal Approximation) method for each group. Percentages will be compared using Chi-Square test or Fisher's Exact test.

Logistic regression will be used to assess the independent contribution of clinical and demographic factors to the estimation of the proportion of patients with COPD who use ICS inadequately. First, univariate and second, multiple logistic regression (MLR) methods will be used to investigate the impact of the following explanatory covariates (patient and disease characteristics) on ICS use.

Potential covariates are:

- Age
- gender
- Smoking history
- Number of exacerbations in the previous year.
- History of asthma (yes/no)
- History of atopy (yes/no)
- COTE index
- COPD GesEPOC 2017 phenotype

Document: \\bcnfs02\general\Hdmgener\MEDICAL AFFAIRS 28.02.2017 actualizada\8. SRO ESTUDIOS\RESPIRATORIO\1237-0070 NIS OPTI\11 - Clinical Trial Report\SAP\SAP - V 1.0\SAP OPTI version1.0 29052019.docx

Author:

Version Number: 1.0

Version Date: [29MAY2019]

Template No.: RWI_TP_BIOS0013 Revision 1

Reference: RWI_WI_BIOS0015

Effective Date: 15Jun2018

Copyright © 2018 All rights reserved. The contents of this document are confidential and proprietary to Holdings Inc. and its subsidiaries. Unauthorized use, disclosure or reproduction is strictly prohibited.

- GOLD 2019 spirometric classifications (1, 2,3, 4)
- GOLD 2019 patient groups (A, B, C, D)
- mMRC score
- CAT - COPD Assessment Test

Backward selection procedures will be applied to generate the final MLR models which consider only covariates in the selection procedure with a p-value <0.1 in the corresponding univariate logistic regression analysis, using inadequate ICS use (yes/no) as response variable. A p-value <0.05 will be used for the covariates to stay in the model in a backward elimination step. Continuous variables can be replaced by categorical variables. Parameters estimated, exp(B) and C95% Wald Confidence Limits for OR will be presented.

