COPD GesEPOC 2017 phenotypes	non-exacerbator, mixed COPD - asthma syndrome (ACOS), exacerbator with emphysema exacerbator with chronic bronchitis		(ref)	
GOLD 2019 spirometric classification	Gold 1 – Mild Gold 2 – Moderate Gold 3 – Severe Gold 4 – Very severe		(ref)	
GOLD 2019 patient groups (A, B, C, D)	Patient A Patient B Patient C Patient D		(ref)	
CAT score (cat)	CAT <10: Low impact of COPD. CAT ≥10: Medium / high impact of COPD		(ref)	
mMRC score	Grade 0 Grade 1 Grade 2 Grade 3 Grade 4		(ref)	
Number of eosinophils (%)	<2% ≥ 2%		(ref)	

Document: \\bcnfs02\general\Hdmgener\MEDICAL AFFAIRS 28.02.2017 actualizada\8. SRO ESTUDIOS\RESPIRATORIO\1237-0070 NIS OPTI\11 - Clinical Trial Report\SAP\SAP - V 1.0\SAP OPTI version1.0 29052019.docx

Author:

Version Number: 1.0

Version Date: [29MAY2019]

Template No.: RWI_TP_BIOS0013 Revision 1

Reference: RWI_WI_BIOS0015

Effective Date: 15Jun2018

Copyright © 2018 All rights reserved. The contents of this document are confidential and proprietary to Holdings Inc. and its subsidiaries. Unauthorized use, disclosure or reproduction is strictly prohibited.

Variable	Category	Inadequate use of ICS	Odds-Ratio (OR)	p-value
Inmunoglobulin E (UI/ml)	<= 100 UI/ml >100 UI/ml		(ref)	
Presence of exacerbations in previous 2 years	None 1-2 exacerbations 3-4 exacerbations 5+ exacerbations		(ref)	
Presence of moderate/severe exacerbations in previous 2 years	None 1-2 moderate/severe exacerbations 3-4 moderate/severe exacerbations 5+ moderate/severe exacerbations		(ref)	
Presence of severe exacerbations in previous 2 years	None 1-2 severe exacerbations 3-4 severe exacerbations 5+ severe exacerbations		(ref)	
Presence of exacerbations in previous year	None 1-2 exacerbations 3-4 exacerbations 5+ exacerbations		(ref)	
Presence of moderate/severe exacerbations in previous year	None 1-2 moderate/severe exacerbations 3-4 moderate/severe exacerbations 5+ moderate/severe exacerbations		(ref)	
Presence of severe exacerbations in previous year	None 1-2 severe exacerbations 3-4 severe exacerbations 5+ severe exacerbations		(ref)	
Antibiotics for COPD exacerbations	No Yes		(ref)	
Oral corticosteroids for COPD exacerbations	No Yes		(ref)	
Type of ICS	ICS alone LABA + ICS LABA + LAMA + ICS			

Inadequate use of ICS: use of ICS without moderate/severe exacerbations in the previous year in patients.

Table 26. Multivariate logistic regression model of inadequate use of ICS (use of ICS without moderate/severe exacerbations in the previous year)

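### SAP 7.2.11 places treated mMRC 2 patients with otherwise low-risk features in both GesEPOC risk classes, so Table 38 adherence is undetermined for ACOS patients and some exacerbators among them

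*SAP*

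**What the plan says.** SAP 7.2.11 defines low risk by four conditions that must all hold: post-bronchodilator FEV1 of at least 50%, mMRC 0 to 2, no more than one exacerbation in the last year, and no hospitalisation in the last year. High risk needs only one of its conditions: FEV1 below 50%, a dyspnoea criterion, two or more exacerbations, or at least one exacerbation with hospitalisation. The dyspnoea criterion reads "mMRC > 2 or mMRC = 2 with treatment or". On treatment, protocol 9.3.1 (repeated in SAP 4.3) states: "Patients in this study will have been prescribed a treatment for their COPD".

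SAP 7.2.14 then uses the class. ICS is indicated for "Patients at high risk and" one of three phenotypes. For ACOS it says "Only mixed phenotype allows the use of ICS as the first option". For the two exacerbator phenotypes, "the use of ICS is indicated after a first treatment of LAMA / LABA, when there is worsening of symptoms". Patients whose ICS status disagrees with this rule are labelled "Non-Adherent to ICS (Inadequate use of ICS)". The result is reported in Table 38, split by exacerbation history.

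Two smaller derivations nearby:
- SAP 7.2.3 and 7.2.4 compute years since COPD and asthma diagnosis as the calendar-year difference plus 1. Tables 9 and 25 group COPD duration as 0–2, >2–5 and >5 years.
- SAP 7.2.5 defines two percentages of change in FEV1, both divided by a predicted FEV1. Table 7 prints both.

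**The concern.** The two risk lists should divide the patients between them, as the neighbouring GOLD A–D rule in SAP 7.2.12 does with a clean cut between mMRC 0–1 and mMRC 2 or more. At mMRC 2 the GesEPOC lists overlap, and the text offers no way out:
- If low risk takes precedence, the mMRC 2 part of the high-risk line never has any effect. Such a patient outside low risk is already high risk through FEV1, exacerbations or hospitalisation.
- If high risk takes precedence and any COPD prescription counts as treatment, the grade 2 in the low-risk line never has any effect, because every study patient is described as having a prescription.

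Two programmers following the SAP could therefore report different adherence for secondary outcome h. The SAP is dated 29 May 2019 and the protocol plans the end of data collection for April 2019. If that timetable was kept, an unwritten tie-break would be chosen with the data in hand.

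**Working it through.** **Overlap.** The inputs are the two lists in SAP 7.2.11. I take treated patients with complete data and read hospitalisation as admission for an exacerbation. The grid is 2 FEV1 classes × 5 mMRC grades × 5 exacerbation states (none; one without or with admission; two or more without or with admission) = 50 profiles. Applying the lists literally:
- both classes: 2 profiles (FEV1 at least 50%, mMRC 2, no admission, 0 or 1 exacerbation);
- neither class: 0 profiles.

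**Effect on adherence.** Applying SAP 7.2.14 to the two overlap profiles under each class:

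| Phenotype | ICS now | If low risk | If high risk |
|---|---|---|---|
| Non-exacerbator | yes | non-adherent | non-adherent |
| Non-exacerbator | no | adherent | adherent |
| ACOS | yes | non-adherent | adherent |
| ACOS | no | adherent | non-adherent if ICS is required, adherent if only allowed |
| Exacerbator, LAMA/LABA-with-worsening condition met | yes | non-adherent | adherent |
| Exacerbator, condition met | no | adherent | non-adherent |
| Exacerbator, condition not met | yes | non-adherent | non-adherent |
| Exacerbator, condition not met | no | adherent | adherent |

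Phenotype comes from the chart (protocol Table 9.3.3:1), so an exacerbator label can coexist with 0–1 exacerbation in the last year. Every overlap patient has 0–1 exacerbation and no admission, so only that column and the Total of Table 38 can change.

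**Size.** For scale, the plan's own precision reproduces: 1.96 × √(0.4 × 0.6 / 900) = 0.032, giving 36.8% to 43.2%. The documents give no count of affected patients, so I work per 10. Let a be the fraction of them on ICS.
- Maximum shift in overall adherence: 10/900 = 1.11 points.
- If ICS is required for high-risk ACOS, users and non-users switch in opposite directions. The net shift is 1.11 × |2a − 1|: 0 at a = 0.5, 0.44 at a = 0.7, 1.11 at a = 0 or 1.
- If ICS is only allowed for high-risk ACOS, only ACOS users switch. For ACOS patients the shift is 1.11 × a: 0.56 at a = 0.5, 0.78 at a = 0.7, 1.11 at a = 1.
- Within the 0–1 exacerbation column, whose size is assumed, the maximum is 10/810 = 1.2 points to 10/450 = 2.2 points.
- A shift as large as the planned half-width would need at least 0.032 × 900 = 28.8, so 29 patients, all switching the same way.

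**Minor (a), time since diagnosis.** If visit and diagnosis dates are spread evenly over the calendar year, the calendar-year difference is right on average, so adding 1 overstates the mean by about 1 year. Individual errors run from about 0 to 2: visit 31 Dec 2018, diagnosis 1 Jan 2016, true 3.0, derived 3; visit 15 Jan 2019, diagnosis 30 Dec 2016, true 2.04, derived 4. Inclusion criterion 3 requires more than 2 years since diagnosis, so the smallest calendar difference is 2 and the smallest derived value is 3. The 0–2 class is empty. Deleting the 1 alone is not enough: with true duration assumed uniform on 2–20 years (2–10 years), misclassified patients rise from 2.8% (6.2%) to 5.6% (12.5%), because some eligible patients then fall in 0–2.

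**Minor (b), FEV1 change.** Example: pre 1.50 L (50% of predicted), post 1.68 L (56%). Predicted FEV1 is 1.50/0.50 = 1.68/0.56 = 3.0 L. Both percentages are 0.18/3.0 = 6.0%. Dividing by the measured pre value would give 0.18/1.50 = 12.0%.

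**The case against.** Several limits on the point stand.
- That no profile meets neither class depends on complete data and on one reading of hospitalisation. The low-risk list refers to any hospitalisation, the high-risk list to an exacerbation with hospitalisation. Read literally, a patient with FEV1 of at least 50%, mMRC 0–1, at most one non-hospitalised exacerbation and an unrelated admission meets neither.
- Two of 50 profiles is a count of logical cells, not of patients.
- The 61% ICS share in the study-size section is no guide to a. It describes non-exacerbators, whose adherence never switches.
- For exacerbators, worsening after LAMA/LABA is not itself defined as a variable, so that part of the indeterminacy rests on a second gap.
- Table D is an image that is not shown. Whether it or the cited guideline settles mMRC 2 cannot be checked here. The SAP text does not.

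A reader might infer more than this. Because SAP 16.1.3.1 models inadequate ICS use ("using inadequate ICS use (yes/no) as response variable") and 7.2.14 uses the same label, one might conclude that Tables 5, 25 and 26 are affected. The documents do not support that as it stands: the tables define the term by exacerbation history alone, as in the Table 25 footnote ("Inadequate use of ICS: use of ICS without moderate/severe exacerbations in the previous year in patients"). One might also conclude that the risk class enters the regression models. It is only an optional covariate in SAP 8.3, and the covariate list in 16.1.3.1, reused in 16.2.2, omits it. SAP Table 2 lists the class, but the Table 9 shell has no row for it.

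On the minor notes, it is fair that the added 1 is a counting convention. It shifts both ICS groups by the same amount, so the group comparison is not biased by it. The extracted text also does not show which duration class is the reference in Table 25.

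**Conclusion.** The contradiction in SAP 7.2.11 is real and the rule cannot be executed as written. It leaves Table 38 adherence undetermined for ACOS patients in the overlap subgroup, and for exacerbator phenotypes in it only where the LAMA/LABA-with-worsening condition is met. Non-exacerbators, the column for two or more exacerbations and the primary proportion in Table 24 are unaffected.

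The number of patients affected is unknown. The bound of 1.1 points per 10 patients assumes 900 analysed. The net shift depends on the ICS share among those affected and on whether ICS is required or only allowed for high-risk ACOS, which 7.2.14 leaves open. This is a defect in one secondary outcome, cheap to remove before analysis. It is not a threat to the primary result.

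Both minor notes also hold: reported mean duration is about 1 year too long and one duration class is empty, and one reversibility figure is printed as two measures, apart from rounding.

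**What to change.** In SAP 7.2.11 the sponsor should reconcile the two mMRC lines with the cited GesEPOC 2017 guideline and define what counts as treatment, so that the classes are mutually exclusive and exhaustive. This review does not say which class is right. In the same edit:
- use one meaning of hospitalisation in both lists;
- add a programmed check that, among patients with complete FEV1, mMRC, exacerbation and hospitalisation data, none meets both definitions or neither;
- report patients with missing components separately.

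Minor:
- (a) In 7.2.3 and 7.2.4 delete the added 1, and together with that replace the three duration classes in Tables 9 and 25 by classes that can be populated, such as the quartiles 7.2.3 already allows.
- (b) In 7.2.5 confirm the intended denominator of the second percentage, then use the measured pre-bronchodilator FEV1 in litres or drop the row from Table 7.

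The cost is a few lines of SAP text, up to three table shells (Tables 7, 9 and 25) and the matching programming. No new data are needed.

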7.2.12 Gold 2019 Classification

According to GOLD 2019 classification, four different types of patients will be considered:

- Patient A:
 - 0 or 1 exacerbations (not leading to hospital admission) and,
 - mMRC 0-1 and CAT < 10
- Patient B:
 - 0 or 1 exacerbations (not leading to hospital admission), and
 - mMRC ≥ 2 or CAT ≥ 10
- Patient C:
 - ≥ 2 exacerbations or ≥ 1 exacerbation leading to hospital admission, and
 - mMRC 0-1 and CAT < 10.
- Patient D:
 - ≥ 2 exacerbations or any ≥ 1 exacerbation leading to hospital admission, and
 - mMRC ≥ 2 or CAT ≥ 10 .

7.2.13 CAT questionnaire score

The CAT questionnaire score will be obtained from the sum of the 8 items that each range from 0 (no symptoms) to 5 points (highest symptoms) (Available at <http://www.catestonline.org/>).

Table C: CAT questionnaire and responses

Item	Symptom	0 option	Range	5 option
1	Cough	I never cough	[0 5]	I cough all the time
2	Mucus	I have no phlegm (mucus) in my chest at all	[0 5]	My chest is completely full of phlegm (mucus)
3	Chest pressure	My chest does not feel tight at all	[0 5]	My chest feels very tight

Document: \\bcnfs02\general\Hdmgener\MEDICAL AFFAIRS 28.02.2017 actualizada\8. SRO ESTUDIOS\RESPIRATORIO\1237-0070 NIS OPTI\11 - Clinical Trial Report\SAP\SAP - V 1.0\SAP OPTI version1.0 29052019.docx

Author:

Version Number: 1.0

Version Date: [29MAY2019]

Template No.: RWI_TP_BIOS0013 Revision 1

Reference: RWI_WI_BIOS0015

Effective Date: 15Jun2018

Item	Symptom	0 option	Range	5 option
4	Dyspnea	When I walk up a hill or one flight of stairs I am not breathless	[0 5]	When I walk up a hill or one flight of stairs I am very breathless
5	Limitation in domestic activities	I am not limited doing any activities at home	[0 5]	I am very limited doing activities at home
6	Social limitation	I am confident leaving my home despite my lung condition	[0 5]	I am not at all confident leaving my home because of my lung condition
7	Sleep	I sleep soundly	[0 5]	I don't sleep soundly because of my lung condition
8	Energy	I have lots of energy	[0 5]	I have no energy at all
	TOTAL		[0-40]	

Missing or missing answers are not allowed to obtain a valid score. Therefore, the score range of this questionnaire ranges from 0 to 40 points. The score will be grouped into two categories:

- CAT <10: Low impact of COPD (Most days are good, the illness prevents the patient from doing one or two things he or she would like, coughing several days a week).
- CAT ≥10: Medium / high impact of COPD in the patient.

On the other hand, the CAT score will be categorized according to the impact of symptoms such as cough, mucus, chest pressure, dyspnea, limitation in domestic activities, social limitation and sleep and energy:

- Low impact: 0 ≤ CAT ≤ 10.
- Moderate impact: 11 ≤ CAT ≤ 20.
- High impact: 21 ≤ CAT ≤ 30.
- Very high impact: 31 ≤ CAT ≤ 40.

7.2.14 Adherence to ICS treatment recommendations according GesEPOC 2017 guideline.

GESEPOC 2017 guideline indicates different treatment options according to risk and COPD

Phenotype, obtained from Figure 4 in “Guía española de la enfermedad pulmonar obstructiva crónica (GesEPOC) 2017. Tratamiento farmacológico en fase estable” in

<http://www.archbronconeumol.org/es-pdf-S0300289617300844>.

Document: \\bcnfs02\general\Hdmgener\MEDICAL AFFAIRS 28.02.2017 actualizada\8. SRO ESTUDIOS\RESPIRATORIO\1237-0070 NIS OPTI\11 - Clinical Trial Report\SAP\SAP - V 1.0\SAP OPTI version1.0 29052019.docx

Author: Version Number: 1.0
Version Date: [29MAY2019]

[figure not shown]
Template No.: RWI_TP_BIOS0013 Revision 1 Reference: RWI_WI_BIOS0015

Effective Date: 15Jun2018

The use of ICS is indicated only in these cases:

- Patients at high risk and,
 - Phenotypes: exacerbator with emphysema, exacerbator with chronic bronchitis or mixed COPD - asthma syndrome (ACOS). Only mixed phenotype allows the use of ICS as the first option. For exacerbator with chronic bronchitis and exacerbator with emphysema, the use of ICS is indicated after a first treatment of LAMA / LABA, when there is worsening of symptoms.

Table D: Treatment COPD scheme according to risk and phenotype

Document: \\bcnfs02\general\Hdmgener\MEDICAL AFFAIRS 28.02.2017 actualizada\8. SRO ESTUDIOS\RESPIRATORIO\1237-0070 NIS OPTI\11 - Clinical Trial Report\SAP\SAP - V 1.0\SAP OPTI version1.0 29052019.docx

Author:

Version Number: 1.0

Version Date: [29MAY2019]

Template No.: RWI_TP_BIOS0013 Revision 1

Reference: RWI_WI_BIOS0015

Effective Date: 15Jun2018

Copyright © 2018 All rights reserved. The contents of this document are confidential and proprietary to subsidiaries. Unauthorized use, disclosure or reproduction is strictly prohibited.

Holdings Inc. and its

[figure not shown]

Figure 4 in “Guía española de la enfermedad pulmonar obstructiva crónica (GesEPOC) 2017. Tratamiento farmacológico en fase estable” (<http://www.archbronconeumol.org/es-pdf-S0300289617300844>)

Taking into account the algorithm of treatment recommendations included in GesEPOC (phenotype) guidelines, we will define patients as:

- Adherent to ICS (Adequate use of ICS):
 - Patients treated with ICS that according to GesEPOC guidelines should have been treated with ICS, or
 - Patients **not** treated with ICS that according to GesEPOC guidelines should **not** have been treated with ICS.
- Non-Adherent to ICS (Inadequate use of ICS):
 - Patients treated with ICS but according to GesEPOC guidelines should **not** have been treated with ICS, or
 - Patients **not** treated with ICS but according to GesEPOC guidelines should have been treated with ICS.

Document: \\bcnfs02\general\Hdmgener\MEDICAL AFFAIRS 28.02.2017 actualizada\8. SRO ESTUDIOS\RESPIRATORIO\1237-0070 NIS OPTI\11 - Clinical Trial Report\SAP\SAP - V 1.0\SAP OPTI version1.0 29052019.docx

Author:

Version Number: 1.0

Version Date: [29MAY2019]

Template No.: RWI_TP_BIOS0013 Revision 1

Reference: RWI_WI_BIOS0015

Effective Date: 15Jun2018

